8.1.4. Storage and Handling

Omegaven bottles will be stored at room temperature at $\leq 25^{\circ}$ C (do not freeze). Damaged or suspect drug will be returned unused to Fresenius-Kabi. Containers should be shaken before use.

8.1.5. Accountability

All supplies for the study will be accompanied by accountability and shipping documents and will be maintained by the CTCA pharmacy and/or the homecare pharmacy. Information recorded on these accountability and shipping documents will include relevant dates, batch numbers, quantities received or dispensed, to whom dispensed, returned drug, and drug lost or damaged. At the end of the study, all used and unused Omegaven will be accounted for. If expired, the remaining drug supplies will be destroyed.

8.1.6. Dose Adjustments

A dose reduction will occur if:

- TG levels rise above 400 mg/dL,
- If evidence of bleeding occurs.

9. ASSESSMENT OF EFFICACY AND SAFETY

9.1. Outcome Variables

Efficacy and safety will be assessed using the following outcome variables:

- Laboratory results
- AEs reported by the patient and/or identified by study personnel
- Resolution of hepatic injury

9.2. Adverse Event (AE) Recording/Reporting

An AE is any untoward medical occurrence in a patient or clinical investigation patient participating in a clinical study and which does not necessarily have to have a causal relationship with this treatment or

clinical study. An AE can therefore be any unfavorable and unintended sign (including abnormal laboratory findings, for example), symptom, or disease temporally associated with the use of the medicinal product, whether or not considered related to the medicinal product.

AEs include illnesses, signs, or symptoms, independent of causality, that appear or worsen during the course of the study. Whenever the investigator is confident of the diagnosis, he/she should group together as a single illness all related signs, symptoms, and abnormal laboratory test results (e.g., cough, rhinitis, and sneezing should ordinarily be reported as "upper respiratory tract infection").

An investigator will promptly review each lab report. Laboratory AEs are defined as clinical laboratory results that are outside of the normal ranges and are deemed clinically significant by the investigator. Clinically significant laboratory results will be recorded as AEs. Laboratory reports will become a part of the patient's study file.

Procedures, such as surgery, should not be reported as AEs or Serious Adverse Events (SAEs). However, the medical condition for which the procedure was performed should be reported if it meets the AE/SAE definition. For example, an acute appendicitis that begins during the AE reporting period should be reported as the AE and the resulting appendectomy noted in comments. In addition, an elective surgery (and any related hospitalization) whether or not there is an existing medical condition should not be reported as an AE.

The AE reporting period for this study begins at the time the first Omegaven infusion is administered and ends at the final study visit. Any abnormal physical examination findings identified during screening will generally be considered part of the medical history and not an AE. A preexisting condition (i.e., a disorder present before the AE reporting period started and noted on the medical history/physical) should not be reported as an AE unless the condition worsens or episodes increase in frequency during the AE reporting period.

All AEs will be recorded in each patient's study file. The following definitions will be applied to AE reports:

Severity		
MILD	Awareness of signs or symptoms, but they are easily tolerated	
MODERATE	Enough discomfort to cause interference with usual activity	
SEVERE	Incapacitating, with inability to work or do usual activity	
Action Taken		
NONE		
TREATMENT OTH	IER THAN MEDICATIONS REQUIRED	
MEDICATIONS RE	QUIRED	
DISCONTINUED	(Study medication permanently stopped)	
Relationship to S	tudy Medication	
NONE	Causal relationship can be ruled out	

NONE	Causal relationship can be ruled out
POSSIBLY	Causal relationship at least reasonably possible, i.e., relationship can't be ruled out
DEFINITELY	Causal relationship is certain

Patients experiencing AEs that result in study drug discontinuation or those experiencing AEs that are present at the end of their participation in the study will receive follow-up until the AE is resolved, attributed to a cause other than study medication administration, or assessed as chronic or stable.

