10.4. Outcomes Analysis

This is a compassionate use study, with no comparator; therefore the endpoints will be descriptively summarized (continuous data will be presented as mean, standard deviation, median, minimum and maximum; categorical data will be presented as number and percentage). All patients who receive any amount of study medication will be analyzed. The outcome evaluations will include:

- Laboratory results Laboratory values will be summarized at baseline and as change from baseline to worst follow-up values.
- AEs reported by the patient and/or identified by study personnel AEs may be categorized into common terms and summarized as incidence and event rates. If there is sufficient data the incidence rates may also be summarized by AE severity and relationship to study medication.
- **Resolution of hepatic injury** Resolution of hepatic injury will be summarized as incidence and if there is sufficient data may also be presented as time to resolution.
- **Days of PN** Days of PN will be summarized.

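### Protocol 9.2 grades laboratory AEs on a symptom-and-activity scale, so the recorded severity of a symptom-free laboratory AE cannot reflect its size

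*Protocol*

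**What the plan says.** Protocol section 9.2 counts laboratory findings within the general AE definition, as an "unfavorable and unintended sign (including abnormal laboratory findings, for example". It then defines laboratory AEs specifically: "Laboratory AEs are defined as clinical laboratory results that are outside of the normal ranges and are deemed clinically significant by the investigator". The next sentence is "Clinically significant laboratory results will be recorded as AEs", and section 4.3.1 gives the same instruction.

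Section 9.2 introduces its grading table with "The following definitions will be applied to AE reports" and makes no exception for laboratory AEs. The lowest of the three severity grades, MILD, reads "Awareness of signs or symptoms, but they are easily tolerated". The middle grade, MODERATE, asks for discomfort great enough to disturb what the patient normally does. The top grade, SEVERE, reads "Incapacitating, with inability to work or do usual activity".

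Section 10.4 then provides for a possible use of the grade: "If there is sufficient data the incidence rates may also be summarized by AE severity and relationship to study medication".

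**The concern.** The scale measures how the patient feels and functions. A laboratory value has neither property, so the grade of a symptom-free laboratory AE carries no information about how abnormal the result is.

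This matters more here than in many studies. Laboratory results head the list of outcome variables in section 9.1, and the synopsis names them as a safety outcome. Patients enter with hepatic dysfunction, and triglycerides are monitored daily. Sections 10.5 and 11.5 plan no data monitoring committee, and section 10.6 sets no numeric safety threshold for the study, so investigator-recorded AEs carry much of the safety record. If AEs are summarized by severity, large hepatic or lipid changes would sit in the lowest row, or in none, beside trivial ones.

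**Working it through.** The protocol gives no figure to reproduce, and no sample-size or error-rate arithmetic applies. The check is to apply the three definitions in section 9.2 to a laboratory AE that is out of range and judged clinically significant, but causes no symptoms and no loss of activity.

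1. SEVERE needs incapacity. Not met.
2. MODERATE needs discomfort that interferes with usual activity. Not met.
3. MILD needs awareness of signs or symptoms. Because the AE definition treats an abnormal laboratory finding as a sign, MILD can be met if awareness includes the investigator's knowledge of the result. If awareness means the patient's own perception, MILD is not met either and no grade fits.

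The laboratory value enters none of the three steps. Two illustrations:

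- **Bilirubin (assumed values).** A symptom-free rise from 3 to 9 mg/dL is a change of 9 − 3 = 6 mg/dL, or 9 / 3 = 3 times the starting value. If judged clinically significant, it gets MILD or nothing. The protocol does not rule such a course out: E.5 excludes bilirubin above 5 mg/dL at entry, and W.6 names a later rise above 5 mg/dL only when it is due to obstruction.
- **Triglycerides.** Sections 4.2.2 and 8.1.6 attach a dose rule to values above 400 mg/dL. If both are recorded as AEs without symptoms, a value just above 400 and one far above it receive the same grade.

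No other section supplies a laboratory grade. Section 4.3.1 leaves clinical significance to the investigator. The triglyceride trigger is a dosing rule and does not set AE severity. Section 9.3 defines seriousness, which is a different attribute. No toxicity scale is cited anywhere.

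Scope: section 4.3.1 lists 11 hematology and 19 chemistry tests, 11 + 19 = 30, any of which could produce a laboratory AE. This counts the tests exposed to the rule. It does not estimate misgraded events, because only results judged clinically significant become AEs and the protocol gives no rate for these.

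**The case against.** The strongest reply is that little depends on the grade, and most of that reply stands.

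- Section 10.4 summarizes laboratory values at baseline and as change to the worst follow-up value, so the bilirubin example would enter that summary as a 6 mg/dL change. The listed statistics (mean, SD, median, minimum, maximum) show an extreme, but they do not count patients who pass a given level.
- The SAE criteria in section 9.3 include important medical events and do not depend on severity. IND reporting in section 9.4.1 depends on an event being serious and unexpected.
- The triglyceride trigger uses the value itself, and the action taken is recorded for each AE.
- Section 9.2 groups laboratory results under a diagnosis when the investigator is confident of one. This helps only when that illness has symptoms.
- Programmed laboratory grades often belong in an SAP, and none is shown here. However, the investigator assigns severity in the patient's study file under the protocol. An SAP could add derived grades but would not change the recorded ones.

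A reader might also infer more than the text supports:

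- **That 9.2 cannot tell worsening from the entry state.** It can. AEs are limited to events that appear or worsen on study, a pre-existing condition counts only if it worsens or recurs more often, and the investigator must judge the result clinically significant.
- **That every liver test starts abnormal.** I.4 asks for one or more of ALP, AST or ALT above three times normal, and/or bilirubin above 2 mg/dL. GGT is not an entry criterion. A patient may enter on ALP alone.
- **That a severity table is firmly planned.** Section 10.4 makes it optional and conditional on sufficient data.
- **That the protocol says such events are MILD.** It does not; this follows from the definitions, and on the stricter reading no grade applies.
- **That serious harm would be hidden.** Seriousness and severity are separate attributes, and the routes above remain open.

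**Conclusion.** The point holds within a narrow scope. As written, section 9.2 gives a symptom-free laboratory AE the lowest grade or none, whatever its size. The recorded severities and any AE-by-severity summary therefore cannot rank laboratory AEs. This is a stated rule that yields an uninformative grade, rather than detail left for an SAP.

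The damage is confined to those two places, and the number of events cannot be estimated from the protocol. The conclusion assumes that the definitions are applied as written and that some clinically significant laboratory results occur without symptoms. It does not depend on which reading of awareness is taken. The change is worth making because it is cheap and laboratory safety is central to this study, but it does not threaten the study's main descriptive results.

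**What to change.** In section 9.2, restrict the present severity scale to clinical AEs and add a numeric rule for laboratory AEs:

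- Use a published toxicity scale such as CTCAE, naming the version, and state how its grades map to MILD, MODERATE and SEVERE if both kinds of AE are to share a table.
- For liver tests, grade by multiples of the upper limit of normal where the patient's pre-dose value is normal, and by multiples of the pre-dose value where that test is already abnormal. Decide this test by test, since I.4 does not make them all abnormal. Multiples of the pre-dose value for everyone would misgrade: rises from 0.3 to 0.9 and from 3 to 9 mg/dL (assumed values) are both threefold.
- Define the pre-dose value as the last one before the first infusion, and write down the cut points.

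In section 10.4, state that if AEs are summarized by severity, laboratory AEs use these grades.

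The cost is a few lines of protocol text and, if the summary is produced, one programmed derivation. Table 2 already collects the blood tests at every visit, so no new procedure is needed. The downside is that more laboratory events will appear as moderate or severe, which a reader of the report should be told to expect.

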4. INVESTIGATIONAL PLAN

4.1. Study Design

This compassionate use study will include patients with advanced cancer requiring PN for long-term nutrition support who have developed PN-induced hepatic injury or who have existing hepatic dysfunction. Therapy with Omegaven will be provided at an initial dose of 0.1 g/kg body weight (1ml/kg) and increased to 0.2 g/kg body weight (2ml/kg) on day 2 or 3 of treatment. For patients > 120% ideal body weight, adjusted body weight will be used. The infusion rate will not exceed 0.5mL Omegaven/kg body weight/hr (corresponding to 0.05g fish oil/kg/hr). Omegaven will be co-administered via a y-site infusion, with containers being changed every 12 hours. The patient may receive other lipids to meet Essential Fatty Acid (EFA) and/or additional calorie needs. Patients will receive the initial infusion of PN containing Omegaven at Midwestern Regional Medical Center (MRMC) in the infusion center to observe for adverse reactions. If an adverse reaction is observed, IV steroids & benadryl will be administered & Omegaven will be discontinued. Patients will continue to receive infusions at CTCA for the first 2 to 3 days of dosing. After tolerance is established, patients will receive treatment at home with Coram. All study patients will have a Screening Visit; Day 1, Day 2 and Day 3 visits; and weekly visits for one month (see Table 2).

					Weekly	Final Study Visit/
Visit:	Screening	Day 1	Day 2	Day 3	Visits	Early Withdrawal
Informed Consent Form	Х					
Inclusion/Exclusion Criteria	Х					
Physical Exam	Х					Х
Vital Signs	Х	Х	Х	х	Х	Х
Medical History	Х					
Blood hematology/chemistry	Х	Х	Х	Х	Х	Х
Triglyceride level monitoring ¹		Х	Х	Х	Х	
Dispense study medication		Х	Х	Х	Х	
Infusion given at MRMC ²		Х	Х			
Infusion given at MRMC or at the patient's home				х	х	
Adverse Events (AEs)		Х	Х	Х	х	Х
Concomitant medications		Х	Х	Х	Х	Х
Education on home PN &		v				
Omegaven		^				
Assess patient compliance				Х	Х	
Clinical supplies accounted for & destroyed						x

Table 2: Study Schedule

¹ Triglyceride level monitoring will occur daily from the time the patient begins Omegaven dosing until Omegaven dosing is complete.

² Infusions will be given at MRMC for 2-5 days, after which the infusions can be moved to the patient's home.

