4.2.4. Day 3 Visit

The Day 3 Visit may occur at the patient's home. At the Day 3 Visit, the following will occur for all patients:

- Vital signs will be taken.
- Blood will be drawn for hematology and chemistry lab panels (see Section 4.3.1).
- Omegaven dosing will occur via continuous infusion at either CTCA or in the patient's home. The Omegaven dose will remain at 0.2 g/kg body weight (2 ml/kg). The infusion rate will not exceed 0.5mL Omegaven/kg body weight/hr (corresponding to 0.05g fish oil/kg/hr).

- AEs and Concomitant Medications since the previous visit will be recorded.
- Drug accountability will be performed by the homecare nurse to assess patient compliance if the patient has received doses in the home without a nurse present.

4.2.5. Weekly Visits During Home Use of Omegaven (up to 4 weeks of treatment)

Patients will be monitored by healthcare nurses during home health visits every week until withdrawal from the study. The first weekly visit will occur 7 \pm 1 days after the first dose, and continue every 7 \pm 1 days thereafter. During these home health visits the following will occur:

- Vital signs will be taken.
- Blood will be drawn for hematology and chemistry lab panels (see Section 4.3.1).
- Omegaven dosing will occur via continuous infusion at either CTCA or in the patient's home. The Omegaven dose will remain at 0.2 g/kg body weight (2 ml/kg). The infusion rate will not exceed 0.5mL Omegaven/kg body weight/hr (corresponding to 0.05g fish oil/kg/hr).
- AEs and Concomitant Medications since the previous visit will be recorded.
- Drug accountability will be performed by the homecare nurse to assess patient compliance if the patient has received doses in the home without a nurse present.

Omegaven will be given for:

- 4 weeks, or
- Until serum bilirubin is < 2 mg/dL, or
- Until normalization in liver function tests.

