5.3. Patient Withdrawal Criteria

Patients may be terminated from the study for the following events and reasons:

- W.1 The patient chooses to withdraw for any reason
- W.2 The Investigator chooses to terminate the patient from the study. Reasons could include:

- a. Occurrence of AEs related to the use of Omegaven; adverse reaction to Omegaven
- b. Patient non-compliance
- c. Patient discovered after enrollment not to have met the protocol entrance criteria
- W.3 Therapy goals are reached: patient able to meet and sustain nutrient needs by oral nutrition
- W.4 Patient lost to follow-up
- W.5 The principal-investigator terminates the study
- W.6 If bilirubin elevates to > 5 mg/dl due to obstruction
- W.7 Requires open surgical procedure
- W.8 Documented progression of liver metastases contributing to worsening of hepatic dysfunction.

If a patient does not return for a scheduled visit every effort should be made to contact the patient. In any circumstance, every effort should be made to document patient outcome, if possible. Patients will only be considered lost to follow-up if study personnel are unable to communicate with the patient or the patient's legally acceptable representative by three telephone attempts and certified letter. Reasons for withdrawal will be specified in the patient's study file, and will include date of discontinuation of investigational product and date of study withdrawal.

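### The Action Taken codes in 9.2 cannot record the dose reduction that 8.1.6 and 4.2.2 require, and that rule is not reconciled with 4.1 or 4.2.3 to 4.2.5

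*Protocol*

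**What the plan says.** **AE coding.** Section 9.2 introduces its code lists with "The following definitions will be applied to AE reports". Under Action Taken it gives four entries: NONE; TREATMENT OTHER THAN MEDICATIONS REQUIRED; MEDICATIONS REQUIRED; and DISCONTINUED, explained as "Study medication permanently stopped".

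**Dose reduction.** Section 8.1.6 is mandatory in tone: "A dose reduction will occur if" either of two things happens, namely "TG levels rise above 400 mg/dL" or "If evidence of bleeding occurs". Section 4.2.2 repeats the same rule and triggers for Day 1.

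**Discontinuation.** Section 4.1 describes the first infusion, given on site under observation. If an adverse reaction is seen, "IV steroids & benadryl will be administered & Omegaven will be discontinued".

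**Scheduled dose.** Section 4.2.3 raises the dose to 0.2 g/kg. Sections 4.2.4 and 4.2.5 then each state "The Omegaven dose will remain at 0.2 g/kg body weight (2 ml/kg". None of the three refers to 8.1.6 or makes an exception for it.

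**Recording and reporting.** Section 10.7 summarizes study drug administration and has departures from the planned dosing schedule documented and summarized. Section 11.1 requires any protocol deviation to be explained in writing to the regulatory authorities. Section 10.4 plans AE summaries by incidence and event rate and, data permitting, by severity and relationship. The synopsis lists a summary of AEs for each patient as a safety outcome.

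**The concern.** The protocol names two safety signals that must change the dose, triglycerides and bleeding, but its AE form has no way to say that the dose was changed. The only study-drug action it can express is a permanent stop. A reader of an individual AE record could not tell that a bleed had led to a lower dose.

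The second part concerns which instruction applies. A bleed during the first infusion could fall under 4.2.2 (reduce) and under 4.1 (discontinue). A patient whose dose has been reduced meets visit sections that state a rising or constant dose with no exception. The same reduction is then required by one section and a departure from another. How it is logged would depend on which section the site had in hand.

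The study has no comparator, and Sections 10.5 and 11.5 plan no data monitoring committee. The individual AE record is therefore a main source of safety evidence.

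**Working it through.** The protocol gives no figure on this point, so there is nothing to reproduce. The check is a comparison of the code list with every section that changes or stops study drug.

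**Step 1: can the codes describe what the protocol requires?**

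| Action Taken code (9.2) | Concerns study drug? | Describes a dose reduction? |
|---|---|---|
| NONE | no | no |
| TREATMENT OTHER THAN MEDICATIONS REQUIRED | no | no |
| MEDICATIONS REQUIRED | no | no |
| DISCONTINUED | yes, permanent stop | no |

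One of four codes concerns study drug, and none of four describes a reduction. Both triggers in 8.1.6 lead to a reduction, so for 2 of 2 triggers the required action has no code. If the event is also treated, MEDICATIONS REQUIRED would be true as far as it goes but still silent on the dose. If reduction is the only action, no code is accurate.

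**Step 2: which events reach the Action Taken field?** Bleeding fits the AE definition in 9.2 directly. A triglyceride value becomes an AE only if the investigator judges it clinically significant. The gap therefore applies to bleeding AEs, and to triglyceride rises so judged, that are managed by reduction.

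**Step 3: does another record close the gap?** Section 10.7 would show the dose given and any departure from schedule. It does not say that the dose change is tied to the AE that caused it. It also does not say whether a reduction under 8.1.6 counts as a departure.

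**Step 4: are the dosing instructions consistent?**

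| Situation | One section | Another section |
|---|---|---|
| Bleeding at the first, observed infusion | 4.2.2: dose reduced | 4.1: Omegaven discontinued, if bleeding counts as an adverse reaction |
| Trigger met on Day 1 | 4.2.2: dose reduced | 4.2.3: dose raised to 0.2 g/kg, no exception |
| Trigger met on Day 3 or later | 8.1.6: dose reduced | 4.2.4 and 4.2.5: dose stays at 0.2 g/kg, no exception |

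In the second and third rows, following 8.1.6 or 4.2.2 departs from the visit text. Under 10.7 and 11.1 that could be documented and explained as a deviation, although the protocol itself requires it.

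**The case against.** The strongest case against runs as follows. Section 8.1.6 is headed as the place for dose adjustments, so it reads naturally as the specific exception to a general maintenance dose; 4.2.4 and 4.2.5 merely lack a cross-reference. Section 4.1 is about reactions during the first infusion, treated with steroids and an antihistamine, and is not aimed at triglycerides. Dose changes appear under 10.7, triglycerides are summarized as change to the worst follow-up value under 10.4, and bleeding is still recorded as an AE with severity and relationship. No summary stated in 10.4 uses Action Taken.

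Much of this stands, and it limits the point. Several stronger readings that a reader might infer are not supported:

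- That reductions will be miscoded, in particular as NONE. No text maps a reduction to NONE, the case report form is not shown, and 9.2 mentions comments. What can be said is that no listed code is right.
- That 4.2.5 prescribes a response to a safety event. It does not; it fixes a dose without an exception.
- That 5.3 adds a further conflict. It lists "Occurrence of AEs related to the use of Omegaven; adverse reaction to Omegaven" among reasons for which the investigator may terminate a patient. That is discretionary and compatible with either rule.
- That tolerability would be overstated. No planned output is built on Action Taken.
- That a code for temporary interruption is also missing. The protocol has no interruption rule for it to match.

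The objection does not remove the missing code, the missing link between the dose change and the AE, or the overlap of 4.1 with 4.2.2 for bleeding at the first infusion. Nor does the exception reading appear in the text. The protocol leaves it to be inferred, and that inference decides whether a reduction is a deviation.

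**Conclusion.** The point holds as a data-capture gap together with a set of unreconciled dosing statements. The Action Taken list cannot correctly record the reduction that 8.1.6 and 4.2.2 require. Section 10.7 may hold the dose change but does not link it to the AE. Separately, 8.1.6 and 4.2.2 are not reconciled with 4.1 or with 4.2.3 to 4.2.5, so a required reduction could also be logged as a deviation.

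The size is modest. Only AEs managed by reduction are affected, and for triglycerides only those judged clinically significant. The protocol gives no expected frequency of reductions, so no patient count is offered. Its background reports no bleeding among 661 patients, but at a mean dose of 0.11 g/kg/day against the 0.2 g/kg planned here, which does not settle the frequency in this population. No planned summary changes; what suffers is the per-patient AE record and the deviation log.

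Two assumptions are made: that the four code rows, read from a broken table, are complete, and that bleeding can count as an adverse reaction under 4.1. The second matters only for the conflict with 4.1. The correction is nearly free and bears on safety, so it should be made.

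**What to change.** 1. In 9.2, add a DOSE REDUCED entry to Action Taken, and have the AE record point to the matching entry in the dosing record.
2. In 10.7, state that a reduction made under 8.1.6 is not a deviation from the planned schedule, and summarize such reductions as part of study drug administration.
3. Reconcile 4.1, 4.2.2 to 4.2.5 and 8.1.6 so that one passage governs the response to an adverse reaction at the first infusion, to bleeding and to triglycerides above 400 mg/dL, and the others refer to it. The clinical team decides which response holds; items 1 and 2 should then follow the rule it settles on.

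The cost is one code list, one sentence in 10.7 and cross-reference wording, carried in one amendment with the IRB approval that 11.2 requires. No visits, tests or patients are added.
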